**Phase 2 Aim: Conduct a trial of the SSM program within two university communities.** The overall aim of this study is to pilot the SSM program, evaluation metrics, implementation strategies, data collection and assessment procedures for a larger implementation trial. Counseling center utilization will be measured for one academic year to obtain a baseline for both sites. One site will be randomly selected and the SSM program will be implemented, while the other site will continue to collect baseline data. After one academic semester, the additional implementation strategies will be incorporated for an enhanced implementation plan, and both study sites will receive the enhanced implementation plan for one semester. During the implementation phases, counseling center utilization and SSM program use, will be tracked.

**Hypothesis 1:** Introduction of the SSM program will impact utilization of counseling center resources, and the use of an enhanced implementation plan will increase program penetration (e.g., app downloads) and strengthen its impact on utilization. We will explore multiple metrics to assess program impact on utilization, and hypothesize the number of appointments for crisis and follow-up will 1) be reduced during implementation relative to pre-implementation and 2) will be reduced in enhanced implementation relative to initial implementation. We will also explore the impact of implementation on seasonal variations in

counseling center utilization, level of depressive symptoms (as measured by the PHQ-9) at intake, and any other evaluation metrics identified during Phase 1.

**Hypothesis 2:** Sustained use of the SSM program will result in reductions in depression and anxiety among individual users, and these reductions will be mediated by increases in mental health literacy, knowledge of mental health care services, and cognitive and behavioral coping skills.

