### **Procedures Involved:**

Monthly data on engagement with counseling center services will be collected from the counseling center’s Titanium Electronic Medical Record (EMR) to serve as a predeployment “baseline” for Phase 2. For the primary outcome of counseling center resource utilization, we will compare the predeployment phase (the 2 semesters prior to program implementation) to the implementation phases. During the predeployment phase, weekly data will be collected from existing service records at the counseling centers at UIC and NIU on new counseling appointments, follow-up appointment, group therapy appointments and crisis appointments. The data will be reported in aggregate and will not include individual personal identifiers. The SSM program will first be implemented in one study site (UIC or NIU – chosen via random selection) using the initial implementation plan (e.g. advertisements, identification of early adopters, identification of student leaders to serve as champions) designed in Phase 1. Data from individual interviews will be gathered from the first study site will inform an enhanced implementation plan. During this third semester, predeployment data will also be collected at Site #2. Then, the enhanced implementation plan, updated based on the semester 3 deployment at Site #1, will be deployed at both study sites and data will be collected for an additional semester. When the implementation begins on each campus, the program will be made freely available to download, and counseling center intake paperwork will be modified to ask students if they used the SSM program which allows for tracking of counseling center referrals while maintaining patient confidentiality. This design allows us to examine: a predeployment phase for both sites, an initial phase of implementation for Site #1, and an enhanced implementation phase for Site #1 and for Site #2. A strength of this implementation design is that it allows for learning within itself by comparing initial implementation strategies with an enhanced implementation plan. This process of learning and adapting is key for effective and sustainable implementation. Staggering the start times of implementation allows for within-site targeted comparisons of effect of introducing the SSM program on utilization of the counseling center in each site, and for an exploration of between-site differences in the impact of the enhanced implementation plan.

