As originally planned for this project, counseling center utilization data were examined using Simulation Modeling Analysis (SMA) for Time-Series data to determine if there were changes in utilization between the pre-implementation and implementation phases. Because we were unable to enact an enhanced implementation strategy during the second semester of program implementation, we examined implementation as a single phase. SMA evaluates the statistical significance of between-phase changes in data streams and also accounts for the presence of autocorrelation (the non-independence of data points in time-series data streams). A phase effect size (Pearson's R) is produced for each phase-comparison that is then compared to a distribution of data streams, using bootstrapping, resulting in an empirical estimate of the probability of the observed effect occurring by chance.

Interviews were transcribed and coded using a thematic analysis approach. The interview transcripts were first reviewed for thematic content. In creating the codebook, coders met to review their initial codes to reach initial consensus and identified the primary themes that were used to create a codebook. Then, a second round of review took place as the coders reviewed the codebook, refined codes as needed, and completed a final round of coding. The coders met regularly throughout the analytic process to discuss these codes with the study principal investigator, check codes between coders, come to consensus, and ensure validity.

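### The utilization analysis yields a correlation and a probability, but no estimate with an interval of the change in appointments that Hypothesis 1 is about

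*Combined protocol and SAP*

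**What the plan says.** Under Procedures Involved, counseling center utilization is the primary outcome, recorded as weekly aggregate counts of new, follow-up, group and crisis appointments. (That section's opening sentence says monthly. I take weekly, which the rest of the section uses.) Hypothesis 1, under Objectives, expects crisis and follow-up appointments to become fewer under implementation, so it is stated as a number of appointments.

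The Statistical Analysis Plan names one analysis of these series, SMA. Pearson's R serves as the measure of effect and "is produced for each phase-comparison that is then compared to a distribution of data streams, using bootstrapping". The only other output is a probability: the comparison is described as "resulting in an empirical estimate of the probability of the observed effect occurring by chance". No mean count by phase, absolute or percentage change, or confidence interval is named for utilization.

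On phases, the Statistical Analysis Plan reports that the enhanced strategy could not be enacted and that "we examined implementation as a single phase". Procedures Involved defines the comparison period as "the 2 semesters prior to program implementation". It adds: "During this third semester, predeployment data will also be collected at Site #2". The updated plan "will be deployed at both study sites and data will be collected for an additional semester". The staggered start is meant to allow within-site comparisons and also "for an exploration of between-site differences in the impact of the enhanced implementation plan".

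**The concern.** The hypothesis asks how much appointment volume changes. The analysis answers a different question: how strongly the weekly count correlates with a phase indicator. That correlation mixes three things: the change itself, the scatter of weekly counts within phases, and the share of weeks in each phase. The scatter includes the seasonal swing that the protocol expects.

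Two consequences follow. First, R and a probability do not tell a counseling center how many appointments were saved or added. Second, if R is not significant, nothing in the output separates a series that rules out a worthwhile reduction from one too noisy to say. With a few semesters per phase, that second outcome is plausible.

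**Working it through.** The plan states no effect size, SD or power for utilization, so there is no figure of its own to reproduce. The check is of what R can and cannot convey.

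**Inputs from the documents.** With implementation as one phase, the planned schedule gives:

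- Site 1: 2 pre-implementation and 2 implementation semesters, so the implementation share is p = 0.50.
- Site 2: 3 and 1 semesters, so p = 0.25. If only the last 2 baseline semesters are used, p = 0.33.

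The Statistical Analysis Plan does not restate the weeks actually analysed at each site.

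**Inputs assumed.** Weekly SDs of 5, 10 and 20 appointments; 15-week semesters; lag-1 autocorrelation 0.3. None of these is in the documents.

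**Formula.** Let d be the change in weekly mean divided by the within-phase SD. For a two-phase indicator,

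R = d·√(p(1−p)) / √(1 + d²·p(1−p)), and inversely d = R / √(1−R²) / √(p(1−p)).

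**Effect of noise.** Take R = 0.30.

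- At p = 0.50, d = 0.30/0.954/0.500 = 0.629. This is 3.1, 6.3 or 12.6 appointments a week for SD 5, 10 or 20.
- At p = 0.25, d = 0.30/0.954/0.433 = 0.726. This is 3.6, 7.3 or 14.5 a week.

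In the other direction, a fixed fall of 10 a week at p = 0.50 gives |R| = 0.71, 0.45 and 0.24 for the same three SDs. One R value therefore covers a four-fold range of changes when the SD is unknown over a four-fold range.

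**Effect of the split of weeks.** Take a fall of 0.5 SD.

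- p = 0.50: 0.250/√1.0625 = 0.243
- p = 0.33: 0.236/√1.0556 = 0.229, which is 5% smaller
- p = 0.25: 0.217/√1.0469 = 0.212, which is 13% smaller

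For d from 0.25 to 2, the loss at p = 0.25 runs from 13% down to 7%. The split has a real but small effect.

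**What a null result leaves open.** The standard error of the difference in weekly means is about SD × √[(1+0.3)/(1−0.3) × (1/n₀ + 1/n₁)].

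- Site 1, 30 and 30 weeks: SD × √(1.857 × 0.0667) = 0.352 SD. The 95% half-width is 1.96 × 0.352 = 0.69 SD.
- Site 2, 45 and 15 weeks: SD × √(1.857 × 0.0889) = 0.406 SD. The half-width is 0.80 SD.

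An observed R of zero would then be compatible with falls of up to about 0.69 SD at Site 1, roughly 3.5 a week at SD 5 or 14 a week at SD 20. At Site 2 the figures are about 4 and 16. The reader cannot recover these limits from R and a probability.

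**The case against.** The strongest reply is that no inference is wrong. SMA tests each series against autocorrelated data streams, and its probability does not depend on R being a good effect measure. The weekly counts exist, so phase means can be computed by anyone who wants them. The Phase 2 Aim describes piloting the program, its metrics and strategies, and "data collection and assessment procedures for a larger implementation trial"; it does not expressly promise an effect estimate for sizing that trial. All of this stands. It makes the gap one of estimation and reporting, not of validity.

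A reader might also infer that the plan makes a faulty comparison of R between sites, distorted by the staggered schedule. The documents do not support that. The between-site look is called an exploration and is tied to the enhanced plan, which was not enacted. The Statistical Analysis Plan specifies phase comparisons and nowhere sets one site's R against the other's. The schedule effect is also small beside sampling error. In simulations of 4,000 streams with 15-week semesters, autocorrelation 0.3 and a 0.5 SD fall, mean R is about −0.25 with 30 and 30 weeks and −0.22 with 45 and 15. That gap of 0.03 compares with a sampling SD of about 0.16 for a single R.

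Lastly, a rate ratio from a phase-only model would not be clean either. Seasonal variation is expected, and Site 2's one implementation semester would be set against baseline semesters of both seasons. This objection stands and shapes the fix.

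**Conclusion.** The point holds as a missing estimate. For the primary outcome, the specified analysis can indicate whether a change is larger than chance, but it cannot say how many appointments it amounts to or which reductions the data exclude. Noise is the main reason: R = 0.30 may mean 3.1 or 12.6 appointments a week at Site 1 for SDs of 5 and 20. The split of weeks adds a 5% or 13% difference for a 0.5 SD fall, depending on how much of Site 2's baseline is used.

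The dependence of R on SD and split is algebraic and needs no assumption. The appointment figures rest on illustrative SDs. The interval widths rest on assumed semester length and autocorrelation. The phase shares come from the planned schedule and may differ from what was run. The SMA significance test stands.

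**What to change.** Keep SMA as the significance test. For each site and appointment type, add:

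- the mean weekly count in each phase;
- the implementation versus pre-implementation rate ratio, or difference per week, with an autocorrelation-robust 95% CI, from a negative-binomial or quasi-Poisson model with a calendar term (for example week of semester, and fall/spring where the data allow);
- the dispersion and the lag-1 autocorrelation;
- the weeks analysed per phase, including how much of Site 2's baseline was used.

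The Statistical Analysis Plan is written in the past tense and presents SMA as the planned method, so label these estimates as an addition to it. Make any exploratory comparison of sites on the rate-ratio or weekly-difference scale, with the caveat that one implementation semester at Site 2 leaves residual calendar confounding that the model cannot fully remove.

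The cost is one extra regression per series and a few lines of text, with no new data. The intervals will be wide, which is itself useful to report.
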